## **Appendix C - Definitions of Adverse Events**

---

#### **Other significant Adverse Events**

#### **Overdose**

## **DEFINITIONS OF ADVERSE EVENTS AND PROCEDURES IN CASE OF PREGNANCY**

It is of the utmost importance that all staff involved in the study is familiar with the content of this section. The Principal Investigator is responsible for ensuring this.

### **Adverse Events**

An adverse event is the development of an undesirable medical condition or the deterioration of a pre-existing medical condition following or during exposure to a pharmaceutical product, whether or not considered causally related to the product. An undesirable medical condition can be symptoms (eg, nausea, chest pain), signs (eg, tachycardia, enlarged liver) or the abnormal results of an investigation (eg, laboratory findings, electrocardiogram). In clinical studies, an AE can include an undesirable medical condition occurring at any time, including run-in or washout periods, even if no study treatment has been administered.

The term AE is used to include both serious and non-serious AEs

### **Serious Adverse Events and suspected unexpected serious adverse reactions (SUSAR)**

It is important to distinguish between Serious Adverse Events (SAEs) and severe adverse events (AEs). Severity is a measure of intensity whereas seriousness is defined by the criteria listed below. An AE of severe intensity need not necessarily be considered serious. For example, nausea which persists for several hours may be considered severe nausea, but not an SAE. On the other hand, a stroke which results in only a limited degree of disability may be considered a mild stroke but would be a SAE.

**A medical emergency usually constitutes an SAE and is to be reported as such**

A serious adverse event is an AE occurring during any study phase (i.e. run-in, pre-entry, screening, treatment, wash-out, follow-up), and at any dose of the investigational product, comparator or placebo, that fulfils one or more of the following criteria:

- results in death
- is immediately life-threatening
- requires in-patient hospitalisation or prolongation of existing hospitalisation
- results in persistent or significant disability or incapacity
- is a congenital abnormality or birth defect

- is an important medical event that may jeopardise the subject or may require medical intervention to prevent one of the outcomes listed above.

For reporting purposes, any suspected transmission via a medicinal product of an infectious agent is also considered an SAE and is reported in an expedited manner. Any organism, virus or infectious particle (for example prion protein transmitting Transmissible Spongiform Encephalopathy), pathogenic or non-pathogenic, is considered an infectious agent.

### **Definitions for severity rating**

0. None – No symptoms
1. Mild - Transient symptoms; awareness of sign or symptom, but easily tolerated. No interference with the subject's daily activities
2. Moderate - Marked symptoms; discomfort sufficient to cause interference with normal activities. Moderate interference with the subject's daily activities
3. Severe - Considerable interference with the subject's daily activities; unacceptable, incapacitating. Inability to perform normal activities

N/A Not Applicable

### **Causal relationship**

The causality of (S)AEs (ie, their relationship to study treatment and/or the investigational procedure) will be assessed by the investigator(s), who in completing the relevant case report form must answer “yes” or “no” to the question “Do you consider that there is a reasonable possibility that the event may have been caused by the drug/the investigational procedure?”

The following terms and definitions are used when assessing the causal relationship between each AE and the relevant trial product(s):

1. Definite - There is no doubt that the incident is related
2. Probable - Good reason and sufficient documentation to assume a causal relationship
3. Possible- A causal relationship is conceivable and cannot be dismissed
4. Unlikely - The event is most likely related to aetiology other than the trial product
5. Not related – The event is not related to the trial product
6. Unknown/Unclassifiable: a report suggesting an adverse event reaction, which cannot be judged because information is insufficient or contradictory and which cannot be supplemented or verified.

N/A Not Applicable

Causal relationship in cases where the disease under study has deteriorated due to lack of effect will be classified as no reasonable possibility.

For SAEs causal relationship will also be assessed for additional study drug and/or other medication and/or study procedure. Note that for SAEs that could be associated with any study procedure the causal relationship is implied as “yes”.

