### **A guide to interpreting the causality QUESTION**

The following factors should be considered when deciding if there is a “reasonable possibility” that an AE may have been caused by the drug.

- Time Course. Exposure to suspect drug. Has the subject actually received the suspect drug? Did the AE occur in a reasonable temporal relationship to the administration of the suspect drug?
- Consistency with known drug profile. Was the AE consistent with the previous knowledge of the suspect drug (pharmacology and toxicology) or drugs of the same pharmacological class? OR could the AE be anticipated from its pharmacological properties?
- Dechallenge experience. Did the AE resolve or improve on stopping or reducing the dose of the suspect drug?
- No alternative cause. The AE cannot be reasonably explained by aetiology such as the underlying disease, other drugs, other host or environmental factors.

- Rechallenge experience. Did the AE reoccur if the suspected drug was reintroduced after having been stopped? A re-challenge would not normally be recommended or supported.
- Laboratory tests. A specific laboratory investigation (if performed) has confirmed the relationship?

A “reasonable possibility” could be considered to exist for an AE where one or more of these factors exist.

In contrast, there would not be a “reasonable possibility” of causality if none of the above criteria apply or where there is evidence of exposure and a reasonable time course but any dechallenge (if performed) is negative or ambiguous or there is another more likely cause of the AE.

In difficult cases, other factors could be considered such as:

- Is this a recognised feature of overdose of the drug?
- Is there a known mechanism?

Ambiguous cases should be considered as being a “reasonable possibility” of a causal relationship unless further evidence becomes available to refute this. Causal relationship in cases where the disease under study has deteriorated due to lack of effect should be classified as no reasonable possibility.

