5.6 Safety Analyses

5.6.1 *Adverse Events*

A summary of subjects reporting at least one of the following AEs will be presented in an overview table:

- Any AE
- Any SAE
- Any treatment-related AE (Definite, Probably and Possible)
- Any treatment-related SAE (Definite, Probably and Possible)
- Any AE leading to discontinuation
- Death

Summaries presenting n (%) of AEs and n (%) of subjects with at least one AE will be provided for:

- All AEs (includes all serious and non-serious AEs)
- All treatment-related AE (Definite, Probably and Possible)
- All SAEs
- All treatment-related SAE (Definite, Probably and Possible)

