8 LISTING OF TABLE, FIGURES AND LISTINGS

8.1 Listing of Tables

Table Number	Table Title
14.1.1	Patient Disposition and Data Sets Analyzed
14.1.2	Screening data (ITT Population)
14.1.3	Preoperative data (ITT Population)
14.1.4	Preoperative samples taken in OR from art and cvc line (ITT Population)
14.2	Concomitant treatments and medications by day (ITT Population)
14.3.1	AKI and corrected creatinine (ITT population)

STATISTISKA KONSULTGRUPPEN		Statistical Analysis Plan
Protocol: The prophylactic effect of Levosimendan in reducing acute kidney injury postoperatively in pediatric patients undergoing corrective heart surgery	Protocol No: MiLe-1	Version: 1.0 Page 17 of 17

14.3.2.1	Hemodynamic parameters by timepoint (ITT population)
14.3.2.2	Arterial blood gas test by timepoint (ITT population)
14.3.2.3	Rate of vasoactive drugs by timepoint (ITT population)
14.3.2.4	NGAL by timepoint (ITT population)
14.3.3.1	Fluid balance by timepoint (ITT population)
14.3.3.2	Morning lab results by timepoint (ITT population)
14.3.3.3	Morning Hemodynamics by timepoint (ITT population)
14.3.3.4	Blood gas at 6 am by timepoint (ITT population)
14.3.3.5	Rate of vasoactive drugs at 06:00 am by timepoint (ITT population)
14.3.3.6	Cardiopulmonary bypass and use of cortisone in OR by timepoint (ITT population)
14.3.3.7	Other parameters by timepoint (ITT population)
14.4.1	Univariable and multivariable analyses of AKI (ITT population)
14.4.2	Correlation analyses (ITT population)
14.5.1	Summary of Adverse Events (Safety Population)
14.5.2	All AEs (includes all serious and non-serious AEs) (Safety Population)
14.5.3	All treatment-related AE (Definite, Probably and Possible) (Safety Population)
14.5.4	All SAEs (Safety Population)
14.5.5	All treatment-related SAE (Definite, Probably and Possible) (Safety Population)

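### SAP treatment-related counts leave out events graded Unknown or given no causality rating, although the protocol treats ambiguous cases as possibly related (minor)

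*Protocol*

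**What the plan says.** Protocol Appendix C, Causal relationship, asks a yes/no causality question and then sets out a graded scale: "The following terms and definitions are used when assessing the causal relationship between each AE and the relevant trial product(s". The grades are Definite, Probable, Possible, Unlikely, Not related and a sixth, "Unknown/Unclassifiable: a report suggesting an adverse event reaction, which cannot be judged because information is insufficient or contradictory". The definition of the sixth grade adds that the report cannot be completed or checked. A not-applicable code follows.

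The causality guide later in Appendix C sets the default for unclear cases: "Ambiguous cases should be considered as being a “reasonable possibility” of a causal relationship unless further evidence becomes available to refute this".

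SAP 5.6.1 builds the overview from lines such as "Any treatment-related AE (Definite, Probably and Possible" and "Any treatment-related SAE (Definite, Probably and Possible". It repeats the same three grades for the detailed summaries, for example "All treatment-related SAE (Definite, Probably and Possible". The titles of Tables 14.5.3 and 14.5.5 in SAP 8.1 carry the same list, for example "All treatment-related AE (Definite, Probably and Possible) (Safety Population". The SAP has no rule, row or footnote for Unknown, not-applicable or missing causality.

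**The concern.** The scale keeps Unknown apart from Unlikely and Not related: it is for a suspected reaction that nobody can judge. The protocol's stated attitude to unclear cases is cautious. The SAP's list is closed, so an Unknown event is handled in the related tables just as an Unlikely or Not related one is. An event with no rating goes the same way.

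At stake is the reported number of treatment-related AEs and SAEs in a small trial in infants. If such events occur, the related counts come out lower than the protocol's default would make them, and no planned table shows that this has happened. Protocol 10.2 promises an individual listing of all adverse events, whereas SAP 8.3 plans an Excel export and no formal listings.

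**Working it through.** The plan gives no figure to reproduce. The check is mainly a comparison of texts.

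**Step 1. What happens to each rating in the SAP tables**

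| Rating | All-AE / all-SAE tables (14.5.2, 14.5.4) | Related tables (14.5.3, 14.5.5) and related lines of 14.5.1 |
|---|---|---|
| Definite, Probable, Possible | counted | counted |
| Unlikely, Not related | counted | not counted |
| Unknown/Unclassifiable | counted | not counted |
| Missing | counted | not counted |

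The third row meets the Appendix C guide only if an Unknown event is an ambiguous one. The protocol does not say so outright. It is the natural reading of a grade defined by insufficient or contradictory information.

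**Step 2. Which scale will the data hold?** The protocol describes causality recording in three ways:

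- yes or no in 7.1.8.1, and yes or no with a specification after yes in Appendix C, Reporting in the Case report Form;
- five grades in the CRF in 7.1.15, running from not related to certain, with no Unknown;
- six grades in Appendix C, Causal relationship, including Unknown.

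The SAP's top grade is Definite, which is the Appendix C term; 7.1.15 uses certain. This suggests that the SAP tabulates the scale containing Unknown, but it does not show what the CRF holds. If the CRF has only the five fields, Unknown cannot be entered and an unjudgeable event would appear as a missing rating.

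**Step 3. Size per patient.** Input: 35 patients per arm (Protocol 10.1, SAP 1.4). Assumption: all 35 receive study drug and so enter the safety population. If k patients in an arm have an Unknown or unrated event and no other related event, that arm's related proportion is lower by k/35:

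- k = 0: 0
- k = 1: 1/35 = 2.9 percentage points
- k = 2: 2/35 = 5.7 percentage points
- k = 3: 3/35 = 8.6 percentage points

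**Step 4. Size relative to the related count.** Let r be the share of events graded Definite, Probable or Possible, and u the share graded Unknown or unrated. The shortfall in the related count is u/(r + u). The documents give neither share, so these values are assumptions that only show how the formula behaves:

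| | u = 0 | u = 0.05 | u = 0.10 | u = 0.20 |
|---|---|---|---|---|
| r = 0.30 | 0% | 0.05/0.35 = 14% | 0.10/0.40 = 25% | 0.20/0.50 = 40% |
| r = 0.20 | 0% | 0.05/0.25 = 20% | 0.10/0.30 = 33% | 0.20/0.40 = 50% |

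The value u = 0 is realistic if raters resolve every unclear case to Possible.

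**The case against.** The strongest reply is that the cautious rule acts before tabulation. The Appendix C guide is addressed to the rater answering the yes/no question. A rater who follows it answers yes to an ambiguous case and would naturally grade it Possible, which the SAP counts. Unknown would then be a small residue of reports that can be neither completed nor checked, and these should be few in closely monitored inpatients. This stands as a reason to expect small numbers. It does not remove the gap: Appendix C still offers Unknown as a separate grade for suspected reactions, and the SAP gives it no place.

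A second reply is that Unknown may not be recordable, given the five CRF fields in 7.1.15. That also stands. It moves the gap to missing ratings and makes reconciling the scales part of the remedy. The guide does not mention missing ratings, so counting them as related is a conservative convention and not something the protocol requires.

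Two stronger readings are tempting, and the documents do not support either.

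- **That these events are counted as unrelated.** The SAP has no table of unrelated events. They are omitted from one subset and remain in Tables 14.5.2 and 14.5.4 and in the exported data.
- **That Unknown grades are likely here because raters are blinded and drug reactions resemble the usual postoperative course.** Protocol 7.1.13 has the code broken for SAEs, so blinding is not a secure premise for Table 14.5.5. The AE definition amendment and SAP 4.5.1 list five AE categories, four of them numeric thresholds, and hypotension is not among them. Under Appendix C, an event with a more likely other cause is Unlikely, not Unknown.

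**Conclusion.** The point holds as a minor one. As written, the SAP leaves any event graded Unknown, or not rated, out of all treatment-related counts. For Unknown events this conflicts with the protocol's default for ambiguous cases, if Unknown is read as ambiguous.

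The total effect cannot be computed, because the number of such events is not given and may be zero. The per-patient figure in the working rests on all 35 patients per arm being treated; the relative shortfalls rest on assumed shares and are not evidence that the problem is large. Nothing in the documents suggests that the omission would favour one arm. The primary analysis and the overall AE and SAE counts are not touched.

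**What to change.** In SAP 5.6.1 and Tables 14.5.1, 14.5.3 and 14.5.5, define treatment-related as Definite, Probable, Possible, Unknown/Unclassifiable or missing causality. Show Unknown and missing in a separate row so that readers can see their weight, and state how a not-applicable code is handled.

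Before database lock, confirm which causality scale the CRF actually uses, and reconcile with it the yes/no, five-grade and six-grade descriptions in the protocol and the grade names in the SAP.

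The cost is a line or two of SAP wording, a changed category list in three tables and one check of the CRF. The small downside is that related counts may be slightly higher.

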**Action taken:**

- 0 None
- 1 Dose of study drug changed
- 2 Study drug temporarily stopped
- 3 Study drug stopped

N/A Not Applicable

**Reporting in the Case report Form**

The following variables will be recorded in the CRF for each AE; description of the AE, the date and time when the AE started and stopped, maximum intensity, whether the AE is serious or not, causality rating (yes or no; if yes specify), action taken with regard to investigational product, AE caused subject to discontinue study and outcome.

**Adverse Events based on signs and symptoms**

All AEs spontaneously reported by the subject or reported in response to the open question from the study personnel: *“Have you had any health problems since the previous visit?”*, or revealed by observation will be collected and recorded in the CRF. When collecting AEs the recording of diagnoses is preferred (when possible) to recording a list of signs and symptoms. However, if a diagnosis is known and there are other signs or symptoms that are not generally part of the diagnosis, the diagnosis and each sign or symptom will be recorded separately.

**Follow-up – Outcome assessment**

Any AEs that are unresolved at the patient’s last AE assessment in the study are followed up by the investigator for as long as medically indicated, but without further recording in the CRF.

The following terms and definitions are used in assessing the final outcome of an AE:

- Recovered - The subject has fully recovered, or by medical or surgical treatment the condition has returned to the level observed at the first trial-related activity after the subject signed the informed consent.

- Recovering - This term is only applicable if the subject has completed the trial or has died from another AE. The condition is improving and the subject is expected to recover from the event.
- Recovered with sequelae - The subject has recovered from the condition, but with lasting effect due to a disease, injury, treatment or procedure. If a sequela meets an SAE criterion, the AE must be reported as an SAE.
- Not recovered - The condition of the subject has not improved and the symptoms are unchanged, or the outcome is not known at the time of reporting.
- Fatal - This term is only applicable if the subject died from a condition related to the reported AE. Outcomes of other reported AEs in a subject before he/she died should be assessed as “recovered”, “recovering”, “recovered with sequelae” or “not recovered”. An AE with fatal outcome must be reported as an SAE.
- Unknown - This term is only applicable if the subject is lost to follow-up

## **Reporting of serious adverse events**

For studies in countries implementing the EU Clinical Trials Directive, informing Ethics Committees and Regulatory Authorities will be performed by the sponsor.

All Suspected Unexpected Serious Adverse Reactions (SUSARs) have to be reported, whether or not considered causally related to the investigational product, or to the study procedure(s). The Clinical Study Serious Adverse Event Report Form will be used together with other relevant supporting documentation (e.g. ECG, laboratory results, autopsy report) and relevant CRF modules. All SUSARs have to be electronically registered in the EMEAs database.

## **FURTHER GUIDELINES ON THE DEFINITION OF A SERIOUS ADVERSE EVENT**

### **Life threatening**

‘Life-threatening’ means that the subject was at immediate risk of death from the AE as it occurred or it is suspected that use or continued use of the product would result in the subject’s death. ‘Life-threatening’ does not mean that had an AE occurred in a more severe form it might have caused death (eg, hepatitis that resolved without hepatic failure).

### **Hospitalisation**

Out-patient treatment in an emergency room is not in itself a serious AE, although the reasons for it may be (eg, bronchospasm, laryngeal oedema). Hospital admissions and/or surgical operations planned before or during a study are not considered AEs if the illness or disease existed before the subject was enrolled in the study, provided that it did not deteriorate in an unexpected way during the study.

### **Important medical event or medical intervention**

Medical and scientific judgement should be exercised in deciding whether a case is serious in situations where important medical events may not be immediately life-threatening or result in death, hospitalisation, disability or incapacity but may jeopardize the subject or may require medical intervention to prevent one or more outcomes listed in the definition of serious. These should usually be considered as serious.

*Examples of such events are:*

- Angioedema not severe enough to require intubation but requiring iv hydrocortisone treatment*
- Hepatotoxicity caused by paracetamol (acetaminophen) overdose requiring treatment with N-acetylcysteine*
- Intensive treatment in an emergency room or at home for allergic bronchospasm*
- Blood dyscrasias (eg, neutropenia or anaemia requiring blood transfusion, etc) or convulsions that do not result in hospitalisation*
- Development of drug dependency or drug abuse*

### **A guide to interpreting the causality QUESTION**

The following factors should be considered when deciding if there is a “reasonable possibility” that an AE may have been caused by the drug.

- Time Course. Exposure to suspect drug. Has the subject actually received the suspect drug? Did the AE occur in a reasonable temporal relationship to the administration of the suspect drug?
- Consistency with known drug profile. Was the AE consistent with the previous knowledge of the suspect drug (pharmacology and toxicology) or drugs of the same pharmacological class? OR could the AE be anticipated from its pharmacological properties?
- Dechallenge experience. Did the AE resolve or improve on stopping or reducing the dose of the suspect drug?
- No alternative cause. The AE cannot be reasonably explained by aetiology such as the underlying disease, other drugs, other host or environmental factors.

- Rechallenge experience. Did the AE reoccur if the suspected drug was reintroduced after having been stopped? A re-challenge would not normally be recommended or supported.
- Laboratory tests. A specific laboratory investigation (if performed) has confirmed the relationship?

A “reasonable possibility” could be considered to exist for an AE where one or more of these factors exist.

In contrast, there would not be a “reasonable possibility” of causality if none of the above criteria apply or where there is evidence of exposure and a reasonable time course but any dechallenge (if performed) is negative or ambiguous or there is another more likely cause of the AE.

In difficult cases, other factors could be considered such as:

- Is this a recognised feature of overdose of the drug?
- Is there a known mechanism?

Ambiguous cases should be considered as being a “reasonable possibility” of a causal relationship unless further evidence becomes available to refute this. Causal relationship in cases where the disease under study has deteriorated due to lack of effect should be classified as no reasonable possibility.

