#### **1.5.4 Dosage and interactions with other medications**

As earlier mentioned, Levosimendan is not registered for use in a paediatric population. In the lack of pediatric and neonatal data, the drug has been used with an adult dosage regimen with successful results, which has been presented above. The adult dosage of Levosimendan is 12 µg/kg loading dose followed by an infusion of 0.1-0.2 µg/kg/min. This is the also the recommendation dose of the pharmacy at Queen Silvias Children's Hospital for use of Levosimendan in PICU. The elimination half-life of Levosimendan is about 1 hour, but there is at least one metabolite that has prolonged effects of about 80 hours. This may account for the observations of sustained benefit after discontinuation of the drug. Levosimendan can be infused simultaneously with any other medications. However, cautious should be taken in case of infusion of arrhythmogenic drugs.

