### 5.1.1 Levosimendan

Levosimendan, a calcium-sensitizer (ATC-kod: C01CX08), has been developed for short-time treatment of de-compensated heart failure and is used intravenously when patients with heart failure require immediate initiation of drug therapy and when conventional therapy is insufficient. It increases cardiac contractility and induces vasodilatation.

The pharmacokinetics of Levosimendan is linear at the therapeutic dose range of 0.05-0.2 µg /kg/minute. The short half-life (about 1 hour) of the parent drug, Levosimendan, enables fast onset of drug action, although the effects are long-lasting. The maximum concentrations of metabolites (OR-1855 and OR-1896) are seen on average 2 days after stopping a 24-hour infusion. It is completely metabolised and negligible amounts of unchanged parent compound are excreted in urine and faeces.

Limited data suggest that the pharmacokinetics of levosimendan in children (3 months - 6 years of age) after a single dose is similar to that in adults.

There are no particular risks with short-term use regarding general toxicity and gene toxicity.

Limited data suggest that the pharmacokinetics of Levosimendan in children (3 months- 6 years of age) after a single dose is similar to that in adults. The pharmacokinetics of the active metabolite has not been studied in children.

No pharmacokinetic interactions have been observed. However, cautious should be taken in case of all arrhythmogenic drugs or those which decrease blood pressure like beta blockades.

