### **5.1.2 Milrinone**

Milrinone is a phosphodiesterase inhibitor (ATC-kod: C01CE02). It is a positive inotropic and vasodilating substance. Milrinone is indicated for short term treatment (up to 35 hours) of pediatric patients with acute heart failure, including permits low output after cardiac surgery.

In published studies, selected doses for infants and children were i.v. loading dose of 50-75 g/kg during 30 to 60 minutes or continuous i.v. infusion initiated on the basis of the hemodynamic response and the potential occurrence of adverse events between 0.25-0.75 micrograms/kg/min for a period of up to 35 hours.

Milrinone eliminates faster in children than in adults and neonates have significantly lower clearance than children. It has a mean terminal half-life of 2 to 4 hours in infants and children

Milrinone is slowly injected intravenously into a large vein to avoid local irritation.

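### The causality guide in Appendix C contradicts itself on dechallenge and, where the dechallenge sentence is followed, risks under-attributing persisting, metabolite-driven events to levosimendan

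*Protocol*

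**What the plan says.** The guide to the causality question in Protocol Appendix C lists factors for the rater, among them time course, known drug profile and dechallenge, which covers stopping or reducing the dose. It then gives three instructions that bear on this point.

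- A reasonable possibility "could be considered to exist for an AE where one or more of these factors exist".
- There is no reasonable possibility "where there is evidence of exposure and a reasonable time course but any dechallenge (if performed) is negative or ambiguous".
- "Ambiguous cases should be considered as being a" reasonable possibility, unless later evidence refutes it.

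The pharmacology is given elsewhere in the protocol.

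- Levosimendan, Section 5.1.1: "The short half-life (about 1 hour) of the parent drug, Levosimendan, enables fast onset of drug action, although the effects are long-lasting". On the metabolites: "The maximum concentrations of metabolites (OR-1855 and OR-1896) are seen on average 2 days after stopping a 24-hour infusion". The same section says that the active metabolite's pharmacokinetics have not been studied in children.
- Levosimendan, Section 1.5.4: "there is at least one metabolite that has prolonged effects of about 80 hours". Section 1.5.3 gives the same duration as a minimum.
- Milrinone, Section 5.1.2: "It has a mean terminal half-life of 2 to 4 hours in infants and children".

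Section 6.1 halves the infusion rate after 24 hours and stops the infusion 2 hours later. Section 7.1.13 ends the infusion and breaks the code when an event is assessed as an SAE or SUSAR. SAP Section 5.6.1 tabulates treatment-related AEs and SAEs as well as all AEs and SAEs.

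**The concern.** A causality guide should lead two careful raters to the same answer on the same facts. This one does not: an event with suitable exposure and timing but an unclear dechallenge is rated no under one sentence and yes under another.

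The sentence that yields no also presumes that a drug effect fades once the drug is stopped. That is a fair presumption for milrinone. It is a poor one for an effect driven by levosimendan metabolites, which by the protocol's own account are still rising a day after the infusion ends. A true reaction of that kind would be expected to persist, so a negative dechallenge says little about its cause. The guide makes no allowance for this.

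Three things depend on the rating: the yes/no causality answer in the CRF, the treatment-related tables (SAP Tables 14.5.1, 14.5.3 and 14.5.5), and whether an unexpected SAE is handled as a suspected reaction under Protocol Section 7.1.11.

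**Working it through.** **1. The guide set against itself.** Take an event with exposure and a compatible time course.

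| Dechallenge result | One-factor sentence | Dechallenge sentence | Ambiguous-case sentence |
|---|---|---|---|
| Ambiguous | may be yes | no | yes |
| Negative | may be yes | no | yes, if the mixed evidence is read as ambiguous |

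The conflict is direct for an ambiguous dechallenge. For a negative one it is softer, because the one-factor sentence is permissive.

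**2. Kinetics after stopping.** Inputs are the half-lives in Protocol Sections 5.1.1 and 5.1.2.

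Fraction remaining = 0.5^(t / half-life). Time to fall below 5% = half-life × log(20)/log(2) = 4.32 × half-life.

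| | Half-life | Below 5% at | Left at 12 h | Left at 24 h |
|---|---|---|---|---|
| Levosimendan parent | 1 h | 4.3 h | 0.02% | below 0.01% |
| Milrinone, short | 2 h | 8.6 h | 1.6% | 0.02% |
| Milrinone, long | 4 h | 17.3 h | 12.5% | 1.6% |

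The levosimendan metabolites reach their average maximum 48 h after stopping, about 24 + 48 = 72 h after the start. At 24 h after stopping, milrinone is almost gone and the metabolites have yet to peak. The parent drug clears faster than milrinone, so the contrast applies only to metabolite-driven effects.

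**3. Range of the effect on counts.** The documents give no rates, so every input here except 35 per arm is assumed. Let the true drug-related rate be 20% in both arms (35 × 0.20 = 7 infants). Let q be the share of these with a negative dechallenge, and w the share of cases in which the rater applies the dechallenge sentence.

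Expected number rated related = 35 × 0.20 × (1 − w × q).

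Milrinone has q = 0.10; levosimendan has q = 0.25, 0.50 or 0.75.

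| w | Levosimendan, q = 0.25 / 0.50 / 0.75 | Milrinone |
|---|---|---|
| 1 (always applied) | 5.3 / 3.5 / 1.8 | 6.3 |
| 0.25 | 6.6 / 6.1 / 5.7 | 6.8 |
| 0 (opposing sentences followed) | 7.0 / 7.0 / 7.0 | 7.0 |

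If levosimendan also has q = 0.10, both arms give 7 × 0.90 = 6.3 at w = 1 and there is no imbalance. If its q is below milrinone's, as could happen with parent-drug reactions, the direction reverses.

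**The case against.** A reader might infer that levosimendan reactions are systematically classed as unrelated and that the safety tables therefore favour the test drug. The documents do not support that, for several reasons.

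- The opposing sentences can rescue a case. The known-profile factor also invites the rater to consider what the drug's pharmacology would predict, which includes a late metabolite.
- The dechallenge sentence applies only if dechallenge was performed. The five AE criteria in the protocol's AE-definition amendment and SAP Section 4.5.1 are read no later than 24 hours after weaning from bypass, during or about the end of the infusion. Late metabolite-driven events largely fall outside them.
- Reactions to parent levosimendan would clear sooner than reactions to milrinone.
- Open milrinone when the rate reduction is not tolerated (Section 6.1), and active treatment of hypotension and arrhythmia (Section 7.1.15), blur dechallenge in both arms.
- The code is broken at an SAE (Section 7.1.13), so the rater may know the drug and allow for its kinetics.
- The SAP tables use the graded scale. Appendix C defines its *possible* grade without a dechallenge test.
- Section 7.1.11 requires all SAEs to be reported whatever their causality rating, and the SAP already tabulates all AEs and SAEs.

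These points stand, and they defeat any claim of demonstrated bias. They do not remove the contradiction. Nor do they fully cut the link to the tables: the Appendix C section on CRF reporting asks for a yes/no answer first and a grade only if the answer is yes, so a no can keep an event out. An unblinded rater could allow for the metabolites, but nothing in the guide says to.

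**Conclusion.** The point holds as an internal contradiction in Appendix C, together with a risk of differential misclassification. The contradiction follows from the text alone and needs no assumption. The risk rests on two conditions: that some raters follow the dechallenge sentence, and that some levosimendan reactions are metabolite-driven and still present after stopping. The documents quantify neither, so the size is unknown, from none to substantial. Figures such as 3.5 against 6.3 related cases illustrate that range and are not estimates.

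The exposure lies mainly in SAEs and in events still present when the infusion stops. For those, the yes/no rating, the treatment-related tables and SUSAR handling can all be affected. The all-causality AE and SAE tables do not depend on the rating.

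**What to change.** In the Appendix C causality guide, delete a negative or ambiguous dechallenge as a ground for finding no reasonable possibility. Add a sentence to this effect: *improvement after the study drug is stopped or reduced may support a causal link, but its absence or an unclear result does not by itself exclude one, because levosimendan metabolites peak about 2 days after the infusion ends.* This reconciles the guide with itself and with Section 5.1.1.

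Do not justify the change by saying that raters are blinded, since Section 7.1.13 breaks the code at an SAE. No new SAP table is needed, because Section 5.6.1 already includes the all-causality summaries.

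The cost is a small edit to one passage and somewhat more events rated as related.
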